Abdominal Pain Questionnaire

The 0-10 point Abdominal Pain Questionnaire (APQ) is an 11-point numeric rating scale to assess the worst abdominal pain on a daily basis. A higher score indicates a greater severity of abdominal pain. The APQ has a recall specification of 24 hours. As with the CDAI, SF and AP, patients are to report their abdominal pain severity using the APQ for 10 days prior to each study visit on a patient diary.

The CDAI, SF and AP scores will be calculated, and the APQ will be completed every 12 weeks and at Study Completion (or Early Withdrawal visit if the patient completed the patient diary); SES-CD assessment will take place at the Week 108 visit or early withdrawal visit.

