4.4.4.4 Ileocolonoscopy with Biopsies

An ileocolonoscopy will be performed at the Week 108 visit or Early Withdrawal visit if prior to Week 108. If the early withdrawal visit occurs after the Week 108 visit, then the ileocolonoscopy with biopsies should be conducted only at Week 108. The ileocolonoscopy should take place on the day of the Week 108 or Early Withdrawal visit or no later than 10 days after the visit. The ileocolonoscopy is being performed to assess the endoscopic change in response to prolonged continuous treatment with etrolizumab.

Patients are to prepare their bowel prior to the ileocolonoscopy procedures with a polyethylene glycol (PEG)-based preparation. Medications used for bowel preparation should be reported on the concomitant medications pages of eCRF.

Each patient entered into the study will have the opportunity to donate a single paired biopsy sample from the ileocolonoscopy procedure. The paired biopsy sample will be stored in the Roche Clinical Repository (RCR) and used in future research for Crohn's disease. Sample donation is optional and requires separate informed consent from the patient.

In consenting patients, the paired biopsy sample should be taken from the terminal ileum during the ileocolonoscopy. Necrotic areas of ulcerated mucosa should be avoided during biopsy sample collection. The paired biopsy sample should be placed in formalin and sent to the central laboratory where it will be paraffin embedded and distributed to the RCR.

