6. STATISTICAL CONSIDERATIONS AND ANALYSIS PLAN

Because of the non-comparative character of the study, no statistical tests are planned; all efficacy parameters will be summarized descriptively. Efficacy in Part 1 (OLE) will be assessed across visits using absolute values and change from baseline for continuous outcomes, and dichotomous data (e.g., CDAI remission, clinical remission) will be evaluated using frequency counts and proportions. Demographic and baseline characteristics such as age, sex, race, region, use of corticosteroids and immunosuppressants, duration of disease, and CDAI, SF and AP scores will be summarized by use of descriptive statistics.

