1.3 OUTCOME MEASURES FOR GA29145 PART 1 (OLE)

1.3.1 Efficacy Outcome Measures

The efficacy outcome measures for this study are as follows:

- Crohn's Disease Activity Index (CDAI) remission assessed at 12-week intervals during GA29145 Part 1 (OLE)
- Clinical remission assessed at 12-week intervals during GA29145 Part 1 (OLE), as defined by a stool frequency (SF) mean daily score ≤ 3 and an abdominal pain (AP) mean daily score ≤ 1 with no worsening in either subscore compared to baseline, averaged over 7 days prior to visit

- Simple Endoscopic Score for Crohn’s disease (SES-CD) score assessed at Week 108 or at early withdrawal, if prior to Week 108, during GA29145 Part 1 (OLE)

The efficacy outcome definitions are provided below.

Table 2 Efficacy Outcome Definitions

Outcome Term	Definition
CDAI	CDAI is a composite of eight assessments: number of liquid or soft stools, abdominal pain, general well-being, presence of complications, taking Lomotil (diphenoxylate/atropine) or other opiates for diarrhea, presence of an abdominal mass, hematocrit, and percentage deviation from standard weight
SES-CD	SES-CD is an endoscopic score derived from four variables (ulcers, ulcerated surface, inflamed surface, and presence of narrowing) that are scored in five ileocolonic segments.
CDAI Remission	CDAI Score < 150
Clinical Remission	An SF mean daily score ≤3 and an AP mean daily score ≤1 with no worsening in either subscore compared to baseline, where the average is taken over 7 days prior to visit

AP= abdominal pain; CDAI = Crohn’s Disease Activity Index; SES-CD= Simple Endoscopic Score for Crohn’s disease; SF = liquid/soft stool frequency.

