1.3.3 Exploratory Outcome Measures

The exploratory outcome measures for GA29145 Part 1 (OLE) of this study are as follows:

- SES-CD ≤ 4 (≤ 2 for ileal patients), with no segment having a subcategory score (i.e., for ulceration size and extent, affected surface, or narrowing) that is > 1 , at Week 108
- Change in SES-CD score between Week 0 (Study GA29144) and Week 108 or early withdrawal (Study GA29145, Part 1; OLE)

Incidence of ATAs to etrolizumab (*de-prioritised from a safety outcome measure and will not be analysed or reported in primary Clinical Study Report [CSR] for GA29145 Part 1 (OLE). See Section 4.4 for details).*

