As endoscopy data is only collected at a common time point of Week 108 during the OLE Study GA21945, continuous SES-CD score will be summarized only at this time point and at parent study Baseline. The handling of patients with partially available segments is detailed in Section 4.1.3, this is not considered as true missing data.

Population: All patients who enrolled into Part 1 of the OLE Study GA29145.

Baseline: The original baseline value from the parent study will be used as the baseline SES-CD score.

Analysis 1 - BOCF

Missing data: If a patient has missing data at a visit (i.e., the assessment was not done), they will be removed from the analysis and no imputation will be performed.

Intercurrent events: No imputation will be performed for treatment withdrawals

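### SES-CD score and change are defined at Week 108 or early withdrawal, but SAP 4.1.3.2 plans only the score at baseline and Week 108, and SAP 4.4 does not record the difference

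*SAP*

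**What the plan says.** The SAP defines the outcomes in two places. Section 1.3.1 lists as an efficacy outcome the SES-CD "score assessed at Week 108 or at early withdrawal, if prior to Week 108, during GA29145 Part 1 (OLE"). Section 1.3.3 lists as an exploratory outcome "Change in SES-CD score between Week 0 (Study GA29144) and Week 108 or early withdrawal (Study GA29145, Part 1; OLE"). Protocol 3.3.1 and 3.3.4 give the same definitions.

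The protocol says how continuous outcomes are to be handled and when the data are collected:

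- Section 6: "Efficacy in Part 1 (OLE) will be assessed across visits using absolute values and change from baseline for continuous outcomes".
- Section 4.4.4.3: "SES-CD assessment will take place at the Week 108 visit or early withdrawal visit".
- Section 4.4.4.4: "An ileocolonoscopy will be performed at the Week 108 visit or Early Withdrawal visit if prior to Week 108". Footnote n of Appendix 1 repeats this.

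The analysis itself is in SAP 4.1.3.2. It opens with the reason "As endoscopy data is only collected at a common time point of Week 108" and concludes that "continuous SES-CD score will be summarized only at this time point and at parent study Baseline". For a patient with missing data at a visit, "they will be removed from the analysis and no imputation will be performed". Treatment withdrawals are not imputed either. The section mentions neither an early-withdrawal score nor a change from baseline.

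SAP section 1 points to section 4.4 for changes from the protocol's planned analyses. Section 4.4 records only the move of anti-therapeutic antibodies to exploratory status.

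**The concern.** A reader of SAP 1.3.1 and 1.3.3 would expect the report to contain a score and a change, with patients who left before Week 108 represented by their exit endoscopy. A programmer following 4.1.3.2 would produce a score at two time points for patients scoped at Week 108, and nothing else. The exit scopes, which patients undergo under the protocol, would then enter no continuous summary, and the listed change outcome would have no specified table.

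What is at stake is whom the continuous endoscopic result describes, and whether the listed outcomes match the reported ones. No hypothesis test or error rate is involved, because SAP 2.1 plans none.

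**Working it through.** No power or sample-size figure applies, so the check sets definition against analysis.

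| Item | Defined or scheduled | Planned analysis |
|---|---|---|
| SES-CD score at Week 108 | SAP 1.3.1 | Yes, SAP 4.1.3.2 |
| SES-CD score at early withdrawal before Week 108 | SAP 1.3.1; scope scheduled in protocol 4.4.4.4 and Appendix 1 | None |
| Change from parent Week 0 | SAP 1.3.3; protocol 6 plans change for continuous outcomes | Not specified |
| Record of a departure | SAP 1 points to 4.4 | None for SES-CD |

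**Is it covered elsewhere?** SAP 4.1.3.1 handles only binary improvement and remission at Week 108. Section 5 says there is no supporting document. The BOCF label on the analysis in 4.1.3.2 matches the segment-level carry-forward rule in 4.1.3. It cannot stand in for withdrawals, because 4.1.3.2 says they are not imputed.

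**Is silence on change just the SAP's style?** It does not look so. Sections 4.2.3.1 and 4.2.3.2 ask for change from baseline by name for laboratory values and vital signs. In 1.3.3, the antibody outcome carries a note that it will not be analysed in the primary report; the SES-CD change outcome carries no such note.

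**Can change be read off the two rows?** Let S be the patients with a Week 108 score, A all patients in the baseline row, and m0 and m108 the mean scores at parent baseline and Week 108. Then

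m108(S) − m0(A) = [m108(S) − m0(S)] + [m0(S) − m0(A)].

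The first bracket is the paired mean change. The second is the baseline difference between scoped patients and everyone in the baseline row. SAP 4.1.3.2 does not say that the baseline row is limited to S, and SAP 4.1.2 separately summarises baseline SES-CD for the whole OLE population. If A is wider than S, the row difference mixes change with patient mix. If A equals S, the mean change is recoverable but its spread is not: the variance of change is s0² + s108² − 2·r·s0·s108, where s0 and s108 are the standard deviations at the two times, and two separate rows do not give the correlation r.

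**Does the stated reason cover the gap?** Exit scopes fall at different weeks, so averaging them with Week 108 scopes mixes durations. That supports separate reporting. It does not bear on change at Week 108, where the timing is common, and it does not explain leaving exit scopes unreported.

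**The case against.** The best defence has five parts.

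1. **The reason is stated.** The sentence about a common time point is fairly read as saying that Week 108 is the only time shared by all patients, which is true. A reader might infer that the SAP wrongly denies that exit scopes exist, but the wording does not require that reading. Clearer wording is enough.
2. **Change is not excluded.** SAP 4.1.3.2 is silent on it. A reader might infer a deliberate decision to drop the outcome. The text supports only that it is unspecified, and the segment rules in 4.1.3, which tie Week 108 to baseline, would suit a comparison with baseline. This stands, but an unspecified outcome still needs specifying.
3. **The SAP supersedes the protocol, and the report is synoptic with limited efficacy data.** Precedence over the protocol cannot reconcile two sections of the SAP. The synoptic statement in section 4 names no omitted outcome.
4. **The exploratory objective is confined to Week 108.** That is so in SAP 1.1, and it fits 4.1.3.2. The outcome definitions in 1.3.1 and 1.3.3 are wider, and the score is listed as an efficacy outcome.
5. **The definition gives one value per patient, at whichever visit applies.** Separate rows are therefore a reporting choice, and the literal outcome is the combined row. This stands, and the fix allows for such a row.

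An added change summary also has a weakness: SAP 4.1.3 uses an adjudicated baseline from up to 3 readers, whereas the OLE score is a local reading only.

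**Conclusion.** The point holds as a mismatch within the SAP. The SES-CD score and change are defined at Week 108 or early withdrawal; the analysis section plans the score at baseline and Week 108 only; and 4.4 is silent. Followed as written, the continuous result describes only patients scoped at Week 108. This assumes that section 4 is the full specification of the analysis, which section 5 supports.

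The effect on the reported means cannot be sized. A reader might infer that leaving out early withdrawals makes the result look better. The documents do not establish this: they give no number of exit scopes and no scores, and patients who left because the sponsor ended Part 1 need not be poor responders. They also do not say whether such an exit triggers the early-withdrawal scope.

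Two features limit the consequence. The study is descriptive. The binary non-responder analysis in 4.1.3.1 already counts withdrawals as failures if the patient could have reached Week 108, apart from exits on or after 15 February 2022. That protects the overall endoscopic picture but does not supply the continuous outcomes. Severity is minor, and the change is a cheap improvement.

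**What to change.** In SAP 4.1.3.2, for patients with both a baseline and an OLE scope:

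- Report SES-CD score and paired change from parent baseline at Week 108.
- Report the same in a separate row for early withdrawal before Week 108.
- In each row give n, the baseline mean of the same patients and the OLE week of the scope.
- Optionally add a combined row matching 1.3.1 and 1.3.3, labelled as mixing time points.
- Label the change as adjudicated baseline against local OLE reading.
- State whether the missing-segment rule in 4.1.3 applies to early-withdrawal scopes.
- Clarify that Week 108 is the only common time point, not the only time at which endoscopy is scheduled.

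If a component is left out on purpose, remove it from 1.3.1 or 1.3.3 and record the reason in 4.4.

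Separately, the missing-segment rule refers to Week 104 where the rest of the section says Week 108. That is an independent slip to correct in the same edit.

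The cost is some SAP wording and one or two table rows. No new procedure is needed, since the exit scope is already scheduled. The downsides are the variable timing of exit scopes and the difference in readers; separate rows and labels deal with both.

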- any segments(s) available at baseline that are not available at Week 108 will result in a non-responder status for the patient for endoscopic improvement/remission. For continuous data the patient's baseline segment score will be carried forward (BOCF) to impute the Week 104 segment score when calculating the total SES-CD score.

4.1.3.1 Endoscopic Improvement and Remission at Week 108

As endoscopy data is only collected at a common time point of Week 108 during the OLE Study GA29145, the endpoints of endoscopic improvement and endoscopic remission will be summarized only at this time point. These endpoints will be examined overall and separated by their previous endoscopic improvement status at their latest visit prior to enrollment into GA29145 i.e., at the parent study's (GA29144) Week 14 or Week 66.

The handling of patients with partially available segments is detailed in Section [4.1.3](#), this is not considered as true missing data.

Population: All patients who enrolled into Part 1 of the OLE Study GA29145.

Baseline: The original baseline value from the parent study will be used to calculate improvement.

Sub-groups:

- All patients overall and split by prior endoscopic improvement status and their prior aTNF exposure status.

Analysis 1 - Non-Responder

Missing data: Patients who are non-evaluable at Week 108 (i.e., could not have reached the maximum visit if they had remained within the program as detailed in Section 4.1.3) will be removed from the analysis. Patients who remain in Study GA29145 but are missing endoscopy scores (i.e., the assessment was not done) will be imputed as non-responders within the analysis, as LOCF is not appropriate when endoscopy data is not collected routinely.

Intercurrent events: Patients who withdraw during Study GA29145 will be set to non-responders using the composite strategy if they could have reached OLE Week 108 at the time of the clinical cut-off date had they not withdrawn from treatment. This excludes patients who withdrew from study drug on or after 15th February 2022.

Analysis 2 - As Observed

Missing data: If a patient has missing data at a visit, they will be removed from the analysis and no imputation will be performed.

Intercurrent events: No imputation will be performed for treatment withdrawals

4.1.3.2 Simple Endoscopic Score for Crohn's disease (SES-CD) score at Week 108

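### The only analysis of the continuous SES-CD score is headed BOCF but is observed-case at patient level, with no analysis that counts withdrawals and no stated baseline set

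*SAP*

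**What the plan says.** SAP 4.1.3.2 covers the continuous SES-CD score and lists one analysis, "Analysis 1 - BOCF". The two rules beneath it are:

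- Missing data: "If a patient has missing data at a visit (i.e., the assessment was not done), they will be removed from the analysis", with no imputation.
- "Intercurrent events: No imputation will be performed for treatment withdrawals".

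The population is "All patients who enrolled into Part 1 of the OLE Study GA29145". On timing, "continuous SES-CD score will be summarized only at this time point and at parent study Baseline". On baseline, "The original baseline value from the parent study will be used as the baseline SES-CD score".

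The term BOCF comes from SAP 4.1.3, under the handling of partially available segments: "For continuous data the patient's baseline segment score will be carried forward (BOCF) to impute the Week 104 segment score". (The week number there does not match the Week 108 visit and can be corrected in the same edit.) Section 4.1.3.2 refers back to that rule and states that a partial endoscopy does not count as truly missing data.

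SAP 1.3.1 defines the efficacy outcome as the score at Week 108, or at early withdrawal if that comes first. SAP 1.3.3 adds the change from parent-study Week 0 to either of those time points. Protocol 4.4.4.4 requires an ileocolonoscopy at an early withdrawal visit that falls before Week 108.

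**The concern.** A table headed BOCF suggests that patients who left were counted as unchanged. Under these rules they are not counted at all.

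The protocol makes selective leaving plausible. Under Protocol 4.3.2, a patient who starts a TNF antagonist, another anti-integrin, an IL-12/23 antagonist or another listed agent must leave Part 1. Patients whose disease needs those drugs are therefore missing at Week 108, and the mean of those who remain can be lower than the baseline mean without any mucosal healing.

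What is at stake is how a listed efficacy outcome is read. No test or error rate is affected, because SAP 2.1 plans none.

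**Working it through.** **1. The rules side by side**

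| Endpoint | First analysis | Second analysis |
|---|---|---|
| Endoscopic improvement and remission (4.1.3.1) | Non-Responder: missing scores and withdrawals count as failures, among patients who could have reached Week 108 | As Observed: missing removed, no imputation |
| CDAI and clinical remission (4.1.3.3) | Hybrid LOCF: missing carried forward, withdrawals count as failures while evaluable | As Observed: missing removed, no imputation |
| Continuous SES-CD (4.1.3.2) | BOCF: missing removed, no imputation | none |

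The content of the third row's only analysis is what the SAP elsewhere calls As Observed.

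**2. Does segment-level BOCF reach an absent patient?** No. It fills a segment that was seen at baseline but not at Week 108. A patient with no Week 108 endoscopy falls under the removal rule.

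**3. Which baseline?** The population line, together with removal for missing data at a visit, can be read as a baseline mean over all enrolled patients. Removal from the analysis can equally mean removal from both time points. The text does not decide.

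**4. Early-withdrawal endoscopies.** They are collected and are part of the outcome measure, but 4.1.3.2 summarizes only Week 108 and baseline. No rule in SAP section 4 says how they are used.

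**5. Possible size.** The plan gives no figure to reproduce, and the documents give no retention, mean or SD for this score. Every input below is an assumption:

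- p = proportion with a Week 108 score, 30% to 90%
- rY = correlation of staying with a lower Week 108 score, 0.2 to 0.4
- rB = correlation of staying with a lower baseline score, 0 to rY
- normal scores, equal SD at both visits, zero true mean change in all enrolled patients

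With k = φ(z(1−p))/p, where φ is the standard normal density:

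- apparent fall against an all-enrolled baseline = rY × k
- part due only to unequal patient sets = rB × k
- apparent fall in the same patients = (rY − rB) × k
- apparent fall under patient-level BOCF = p × (rY − rB) × k

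At p = 0.5, k = 0.3989/0.5 = 0.798. With rY = 0.4 and rB = 0.2:

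- all-enrolled baseline: 0.4 × 0.798 = 0.32 SD
- same patients: 0.2 × 0.798 = 0.16 SD
- patient-level BOCF: 0.5 × 0.16 = 0.08 SD

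A simulation of 2 million draws for this case gave 0.319, 0.161 and 0.081.

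| p | k | All-enrolled baseline, rY 0.2 / 0.4 | Same patients, rY 0.4, rB 0.2 | Patient-level BOCF, rY 0.4, rB 0.2 |
|---|---|---|---|---|
| 30% | 1.159 | 0.23 / 0.46 | 0.23 | 0.07 |
| 50% | 0.798 | 0.16 / 0.32 | 0.16 | 0.08 |
| 70% | 0.497 | 0.10 / 0.20 | 0.10 | 0.07 |
| 90% | 0.195 | 0.04 / 0.08 | 0.04 | 0.04 |

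The same-patient fall runs from 0 (rB = rY) to the full all-enrolled value (rB = 0). A matched baseline removes the part due to unequal patient sets. Selection on the Week 108 score remains.

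**The case against.** The best defence is that the label has a source. SAP 4.1.3 defines BOCF for this score at segment level, 4.1.3.2 refers to it, and the lines under the heading say openly that missing patients are removed and withdrawals are not imputed. That stands in part. This is a misleading label, and a reader might infer an unexplained contradiction that is not there.

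A reader might also infer that the plan sets the Week 108 mean beside a baseline mean of all enrolled patients. The documents do not establish this. Near-identical population wording heads the other efficacy blocks, including their As Observed analyses, and the change score in SAP 1.3.3 is within-patient by nature. It is an ambiguity to resolve.

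Nor do the documents show that those who leave are mostly treatment failures. Protocol 4.5.1 and 4.5.2 list consent withdrawal, pregnancy, infection, malignancy and hypersensitivity as well. Protocol 4.3.1 lets worsening patients add corticosteroids or immunosuppressants and stay. The sponsor also closed Part 1. Selective leaving is a mechanism the protocol allows, of unknown strength.

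Finally, the study is descriptive, the report is synoptic with limited efficacy data (SAP 4), and the binary endoscopic endpoints have a Non-Responder analysis. This limits the overall risk, but it does not correct a mean reported on its own.

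**Conclusion.** The concern holds in this form. The sole continuous SES-CD analysis is observed-case at patient level under a BOCF heading. It lacks the withdrawal-counting analysis that the other efficacy endpoints have, leaves the baseline set unstated and gives early-withdrawal scores no place.

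Selection can bias the summary under either reading of the baseline, so the finding does not depend on that ambiguity. The illustrative sizes rest wholly on assumed retention and correlations. They are small at 90% retention and reach 0.46 SD at 30% with an all-enrolled baseline. Patient-level BOCF reduces the apparent fall in the worked case but does not remove it, and it carries its own assumption that leavers are unchanged. The point is worth correcting before reporting, but it does not threaten the study's main safety purpose.

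**What to change.** In SAP 4.1.3.2:

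1. Rename Analysis 1 'As Observed (segment-level BOCF)'.
2. Show baseline, Week 108 and change in the same patients, with n.
3. Add one sensitivity analysis among patients who could have reached Week 108 under the evaluability rule in 4.1.3. Counting 108 weeks (756 days) back from 15 May 2022, that means OLE Day 1 on or before 19 April 2020, before any visit window. For a patient without a Week 108 score, use the early-withdrawal SES-CD where one exists and otherwise carry the baseline score forward. Keep patients stopped by sponsor termination after 15 February 2022 as observed, as 4.1.3 does.

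Using early-withdrawal scores first matters, because plain patient-level BOCF would overwrite observed endoscopies with an older parent-study value. The 0.08 SD above is for plain BOCF and does not predict the result of this analysis.

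The cost is SAP wording and a table row or two, with no new data. The downsides are that the reported fall would probably be smaller, and that early-withdrawal scores come from mixed time points, which a footnote should state.
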